### **13.5. Missing Data Approach**

Missing data will be minimized by chart abstraction, as feasible, for missing covariates of all models. Missing data will be reported with number and proportion in summary statistics. For statistical model, where data was not captured, it will be assumed Missing at Random (MAR) and will be imputed as the median value among observed subjects, within strata of dose.

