6.2.3. Association of Metformin with Longevity in Small Clinical Trials

Recently, there have been multiple prospective clinical trials exploring the effect metformin in non-diabetic and diabetic patients. Patients were treated with standard clinical doses of metformin ranging from 250mg-2000mg three times days from 14 days to 48 weeks continuing to demonstrate an excellent safety profile. The metformin was very well tolerated with the primary side effect (30-60% of subjects) was self-limited gastrointestinal discomfort including mild diarrhea and anorexia^{1,13,14}. Across multiple disease states, metformin has been shown to decrease appetite stimulating glucagon like peptide-1, decrease low density lipid profiles, decrease the mitotic rate in breast cancer, and improve liver pathology in patients with non-alcoholic steatotic hepatitis^{1,3,13,15-17}. As discussed above, some of these changes are attributed to the anti-glycemic and anti-tumor effects of metformin, yet the anti-inflammatory role cannot be underestimated. However, the effects of metformin on non-diabetics and longevity remain unexplored.

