8.3.9. Collection of questionnaires

To examine cognitive and/or motor changes over the course of the study, subjects may complete a series of questionnaires. All subjects participating in this domain will be scheduled to have questionnaires completed via telephone interaction prior to their surgery and 30 days (+/- 7 days) after their index surgery.

The following questionnaires should be completed during the telephone call prior to the index surgery:

- EQ-5D (quality of life)
- MoCA-BLIND
- Functional Activities Questionnaires (FAQ)

The following questionnaires should be completed during the 30-day telephone call:

- Post-discharge resource use questionnaire
- EQ-5D (quality of life)
- Return to work questionnaire

In order to assess motor function, up to 1/3 of subjects who are over the age of 65 and living within 20 miles of the primary research offices may be asked to attend a 90 day (+ 28 day) in-person visit (Motor Assessment Group). This visit should include questionnaires similar to those completed during the 30-day telephone call as well as motor assessments, specifically:

- Post-discharge resource use questionnaire
- EQ-5D (quality of life)
- Return to work questionnaire
- Functional Activities Questionnaires (FAQ)
- NIH Toolbox
 - Cognition Battery
 - 2 Minute Walk Test
 - Grip Strength

On a case-by-case basis, the study team may determine it best to collect these questionnaires via telephone interaction.

For those subjects who do not attend the 90 day in-person visit, the following questionnaires will be completed via telephone interaction at 90 days post-op (+ 28 days):

- Hospital readmission questionnaire (primary endpoint)
- EQ-5D (quality of life)
- Return to work questionnaire
- Functional Activities Questionnaires (FAQ)
- Cognitive battery (MoCA-BLIND, Hayling, and phone CAM)

To avoid in-study learning by patients, alternative versions will be administered for those questionnaires used at multiple timepoints.

If someone should indicate by their answer on the EQ-5D that they are extremely anxious or depressed, a member of the LTOC team will ask if the subject has discussed these feelings with their health care providers. If yes, no further action is taken.

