## **8. ANALYSIS POPULATIONS**

All participants who were randomized and underwent a surgical intervention within 365 days of randomization will be considered in our analysis population.

- SPRY intention to treat (ITT): This population consists of all patients enrolled and randomized to any treatment dose and duration. This population will only include those who underwent a surgical intervention at any time in the 365 days following randomization. All comparisons will be made based up the randomization table allocated treatment.
- SPRY per protocol analysis (PPA): This population consists of all patients enrolled and randomized who also completed randomization table allocated treatment and underwent a surgical intervention within 365 days of enrollment. Adherence to the protocol is determined by those who confirmed compliance with study drug at their 90-day postoperative evaluation with the study team. Compliance is defined by the verbal confirmation of study drug completion at the 90-day follow up timepoint.

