### 9.2. Secondary Endpoints

Secondary domain-specific outcome measures include information about EHR based alerts reported during the index elective surgical admission, perioperative outcomes, and surgical outcomes.

Specifically, they include:

- Perioperative outcomes (enrollment to postoperative 90 days)
  - Gastrointestinal intolerance (dichotomous; present/absent)
  - SAE as defined in Core Protocol (mild, moderate, severe, life threatening/disabling; adjudicated as related, possibly related, unrelated)

- Surgical outcomes
  - Index admission
    - Postoperative intensive care unit (ICU) admission (dichotomous; any admission/none)
    - ICU length of stay (LOS; continuous, days)
    - Hospital LOS (continuous, days)
    - Discharge disposition (categorical; Home, SNF/LTAC, Death/Hospice)
    - In-hospital mortality (dichotomous; yes/no)
  - 30-day outcomes
    - Organ failure free days (i.e., vasopressor exposure, hemodialysis, or mechanical ventilation; continuous, days)
    - Surgical site infection, as defined by NSQIP and the CDC (categorical)
    - Surgical site occurrence, as defined by Ventral Hernia Working Group (categorical)
  - 90-day outcomes
    - Reoperation/reintervention, both incidence and total number (dichotomous, time to event; any/none and continuous, number)
    - Readmission (dichotomous, time to event; any/none, days)
    - Venous thromboembolic events including deep vein thrombosis and pulmonary embolus after surgery (dichotomous, time to event; any/none, days)
    - Mortality (dichotomous, time to event; yes/no, days)

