## 13. ANALYTIC APPROACH

Primary inferential analyses will be done using a Bayesian approach. Sensitivity analyses will be conducted using both Bayesian and Frequentist approaches, as described. Secondary endpoints will be analyzed using frequentist approaches. A summary of the analyses methods is provided below. For all frequentist models, statistical significance will be defined as a one-sided p-value of <0.025, and for all Bayesian models a one-sided posterior probability > 0.975. If stable inference cannot be made due to sparseness of data within strata/categories, data may be further collapsed as needed.

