Within this model we assume that the underlying distribution of HFD-90 is different within each stratum,  $g$ , and these differences across strata can be explained by a proportional log-odds ratio shift in the HFD-90 distribution,  $\alpha_g$ . Stratum are defined in Section 7. Furthermore, we assume that the effects of each intervention within each pre-op duration are constant across strata and can be explained by a proportional log-odds ratio shift in the HFD-90 distribution  $\theta_{t,d}$ . Where a log-odds ratio  $\theta_{t,d} < 0$  results in an increase in expected HFD-90. For identifiability we assume the effect of placebo across all durations is zero,  $\theta_{1,d} = 0$  for all  $d = 1:3$ . As such, the values of the inverse logit of  $\gamma_c$  define the cumulative probabilities for each HFD-90 value under placebo, common across pre-op durations, and averaged across all strata. For all doses of metformin, we assume that the log-odds ratio of the effect of the dose is dependent on the pre-op duration and takes on the following form:

$$\theta_{t(i), d(i)} = \beta_t + \kappa_d \quad \text{for } t = 2, 3, 4 \text{ and } d = 1, 2, 3.$$

Here,  $\beta_t$  is the log-odds ratio due to the dose and  $\kappa_d$  is the log-odds ratio due to the duration. Under the primary analysis where we pool across all pre-op durations we assume  $\kappa_d = 0$  for all pre-op durations,  $d = 1:3$ .

The prior distribution of  $\gamma_c$  is specified on the probability scale:

$$\pi \sim \text{Dirichlet}(\alpha_1, \dots, \alpha_{90});$$

$$\gamma_c = \text{logit} \left( \sum_{i=-1}^c \pi_i \right);$$

With hyper-parameters,  $\alpha_h$ , specified based on the observed rates of HFD-90 across all strata in pre-trial data (discussed in Section 4) and providing 1 patient worth of information so that  $\sum_{h=1}^{90} \alpha_h = 1$ .

For the strata-specific log-odds ratios we place a normal prior distribution with mean 0 and standard deviation 2:

$$\alpha_g \sim N(0, 2^2).$$

Under the primary analysis, we assume a hierarchical distribution for the dose-effects centered around a common mean so there is borrowing of information across doses:

$$\beta_t \sim N(\mu_\beta, 5^2) \text{ for } t = 2, 3, 4;$$

$$\mu_\beta \sim N(0, 1).$$

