## 13.2. Analytic Approach for Secondary Endpoints

### *Primary Analysis*

The analysis of secondary endpoints will be conducted with Frequentist methods using unadjusted linear regression, logistic regression, and Cox models for continuous, dichotomous, and time-to-even secondary endpoints, respectively on both the ITT and PPA populations. Secondary endpoints are described in section 9.2 above. Treatment arms will be pooled across all durations and doses to form treated vs. placebo groups, with the placebo group used as the reference category in all analyses. There will be no adjustment for covariates, other than treatment arm.

The model structures will mimic the approach used in the frequentist analysis of the primary endpoint above. Specifically:

Linear regression:

$$y_i = \beta_0 + \beta_i * tx\_arm_i + \varepsilon_i;$$

Logistic regression:

$$y_i = \text{logit}(\beta_0 + \beta_i * tx\_arm_i + \varepsilon_i);$$

Cox Regression:

$$h(t|x_i) = h_0(t) * \exp(\beta_i * tx\_arm_i);$$

Where:

$y_i$  or  $h(t|x_i)$ : Secondary outcome of interest for subject  $i$

$\beta_0$  or  $h_0(t)$  = Coefficient for intercept or baseline hazard estimate

$\beta_i$  = Coefficient(s) for treatment(s) vs. placebo

$\varepsilon_i$  = Residual Error for Subject  $i$  (i.e. Subject-level random/residual error)

Statistical significance will be defined as an unadjusted  $p < 0.025$ . For all models, outputs will be reported using standard conventions and will include regression coefficients, standard deviations, confidence intervals, test statistics, and p-values, as relevant to each model. Model outputs will be reported both graphically and in tables, as described in sections 10 and 13.10.

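### SAP 13.5 as worded fills missing outcomes with the dose-arm median and analyses them as observed, which MAR does not justify and which can inflate one-sided error

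*SAP*

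**What the plan says.** SAP 13.5 has two separate instructions. The first uses chart abstraction to reduce missing covariates. The second concerns data not captured for the statistical model: "it will be assumed Missing at Random (MAR) and will be imputed as the median value among observed subjects, within strata of dose". The second names neither covariates nor outcomes. Section 13.5 describes no multiple imputation, variance correction or missing-data sensitivity analysis.

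Other sections show what the rule can reach:

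- SAP 13.2, secondary endpoints: "There will be no adjustment for covariates, other than treatment arm".
- SAP 13.1: the HFD-90 models use only arm, surgical stratum and pre-operative duration. Stratum is nominal and has no median. The model text states that "we assume that the underlying distribution of HFD-90 is different within each stratum".
- Protocol 8.3.9: patients who do not attend the 90-day visit are telephoned, and the call includes the "Hospital readmission questionnaire (primary endpoint").
- SAP 8, per-protocol population: "Adherence to the protocol is determined by those who confirmed compliance with study drug at their 90-day postoperative evaluation".
- SAP 13: success is "for all Bayesian models a one-sided posterior probability > 0.975", or a one-sided p-value below 0.025 in frequentist models.

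**The concern.** MAR permits inference from the observed data given the variables that explain the missingness. It does not permit entering one fixed value per arm as though it had been measured. Four consequences follow.

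1. **Uncertainty.** The analysis counts imputed patients at full weight. If the observed arm medians differ by chance, every imputed patient repeats that difference and it reads as a treatment effect.
2. **Stratum.** The fill depends on dose only, while the primary model assumes that HFD-90 differs between surgical strata. If loss depends on stratum and arm, the fill biases the comparison.
3. **Deaths.** A missing patient cannot receive the score of −1 unless about half the arm died.
4. **Dichotomous endpoints.** The median is the majority class. For an uncommon event every missing patient becomes event-free, so the arm with more missing data looks safer. Near 50%, the fill can flip between arms.

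A patient with no 90-day contact cannot be confirmed compliant. Imputed HFD-90 values would therefore fall mainly in the ITT analysis.

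**Working it through.** **The plan's own figure.** 1 − 0.975 = 0.025, so the Bayesian and frequentist thresholds agree. The documents give no analysed sample size, HFD-90 distribution or missing rate to reproduce.

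**Inputs from the SAP.**

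- Allocation √3:1:1:1 (section 6): placebo 1.732/4.732 = 36.6%, each dose 21.1%.
- Cumulative logistic model with α_g ~ N(0, 2²), β_t ~ N(μ, 5²), μ ~ N(0, 1) and κ = 0 (section 13.1). The duration sensitivity model prints an SD of .5, so 0.5 was also run for dose.

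**Assumptions.** N = 400 (the trial stopped before the interim look planned at 500), six strata with log-ORs from −0.4 to 0.5, the HFD-90 shapes and the missing rates. Data are missing completely at random unless stated. Half-integer medians were rounded down; the SAP has no rule for them.

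**Step 1: shift from unequal loss, by arithmetic.** Take an event with true rate p below one half and missing fraction m. The filled rate is p(1 − m). With 10% missing on placebo and 20% on metformin, and no true effect:

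- p = 0.10: 0.090 against 0.080; OR = (0.080/0.920)/(0.090/0.910) = 0.88.
- p = 0.30: 0.270 against 0.240; OR = (0.240/0.760)/(0.270/0.730) = 0.85.
- HFD-90 with 66% at 90, so the fill is 90. The share below 90 becomes 0.34 × 0.90 = 0.306 against 0.34 × 0.80 = 0.272; OR = (0.272/0.728)/(0.306/0.694) = 0.85 in favour of metformin.

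Simulated error for the two dichotomous cases (logistic Wald test, 20,000 trials) was 5.2% and 9.9%. With balanced loss of 10–20% and p = 0.10, error stayed at 1.9–2.6% per side. Rates only shrank, to 9.0% and 8.0%.

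**Step 2: SAP Bayesian model, no true effect.** Per-dose probability of declaring benefit, 6,000 trials per setting, normal approximation to the posterior:

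| Assumed HFD-90 shape | Missing | Error under 13.5 |
|---|---|---|
| Median 87, IQR 84–88, 3% deaths | 2% | 2.9% (2.5% with prior SD 0.5) |
| same | 5% | 3.8% (3.3%) |
| same | 10% | 5.2% (4.7%) |
| same | 20% | 10.1% (9.5%) |
| 58% at 90 | 10% | 4.0% benefit, 6.4% harm |
| 66% at 90 | 10–20%, balanced | 2.4–2.5% |
| 66% at 90 | 10% placebo, 20% metformin | 7.3% |

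Leaving missing values out gave 2.3–2.8% throughout. For the first shape, the chance that at least one of three doses looked beneficial was 6.6% without imputation, 12.6% at 10% missing and 22.4% at 20%. Against MCMC with a one-patient Dirichlet prior on 12 data sets, all 72 threshold decisions agreed.

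**Step 3: pooled metformin against placebo, rank test.** The first shape gave 3.9%, 5.4% and 10.7% at 5%, 10% and 20% missing. With 66% at 90 the figures were 2.5%, 2.7% and 2.3%, rising to 11.8% at 10% against 20% missing. Observed cases only gave 2.2–3.0%.

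**Step 4: separate simulation, stratum-adjusted proportional odds.** Pooled comparison, 1,500 trials per setting:

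- Three shapes without a strong ceiling: 3.5–4.2%, 4.7–5.9% and 11.0–12.3% at 5%, 10% and 20% missing. At 20% the reported SE was 0.184–0.187 against a true SD of 0.299–0.304, about 38% too small (1 − 0.184/0.299 = 0.38).
- 70% at 90, balanced: 2.7–3.4%; SE 0.252 against 0.259 at 20% missing.
- Loss of 30% in high-risk strata on metformin and 10% elsewhere: 16.5–19.8% in all four shapes, log-OR bias −0.12 to −0.24. With the pattern reversed, bias was +0.12 to +0.22 and error 0.3–3.1%.

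**Step 5: the replacement.** In that simulation, leaving missing HFD-90 out of the likelihood gave 2.1–3.3% in every scenario that was completely random or MAR given arm and stratum. In the Bayesian model, with metformin loss of 30% in the two worst strata and 5% elsewhere and placebo loss of 10%, it gave 2.6%; the 13.5 rule gave 7.5%. When loss depended on the outcome itself (35% among poor outcomes on metformin, 10% otherwise), error was 15–22% without the fill and 31–43% with it.

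**The case against.** **Scope.** Section 13.5 opens with covariates, and its second instruction does not name outcomes. A median is undefined for nominal outcomes and does not handle censoring, which suggests outcomes may not have been in mind. The frailty subgroup in SAP 13.3 gives a covariate reading some content. It remains true that reaching outcomes is a reading. But the covariate wording sits in the chart-abstraction sentence, the secondary models have no covariates, and nothing excludes outcomes.

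**Shape.** The largest balanced-loss figures use a shape without a strong ceiling. SAP 13.1 also models HFD-90 = 90 against any other value, and SAP 13.3 lists same-day surgery. Both hint at many patients at 90, where balanced loss does no material harm and the SE is barely affected. This stands.

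**Direction.** No differential missing rate is documented. Poor drug tolerance (SAP 4) makes arm-related loss plausible but does not fix its direction. Swapping the arms in the 66%-at-90 rank test moved the error to the harm side, at 10.2–11.1% in two separate runs. The bias favours whichever arm loses more.

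**Gastrointestinal intolerance.** Protocol 6.2.3 reports that "the primary side effect (30-60% of subjects) was self-limited gastrointestinal discomfort" in earlier metformin trials. Balanced loss gave error of 10–19% per side at 10% missing and 13–31% at 20%, but only when both arms had true rates of 45–55%. Equal rates are an unlikely null for a known metformin effect, and no other endpoint is shown to lie there. Those figures illustrate the mechanism only.

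**Amount missing.** SAP 11 includes health-record data, so HFD-90 need not rest on the telephone call alone, and missingness may be small.

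**Conclusion.** The point holds. As worded, the rule covers outcomes, and a fixed dose-arm median analysed as observed data is unjustified even if MAR is true. Confidence in that is high.

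The size for this trial is unknown, because N, the HFD-90 shape and the missing rates are all assumed. Harm is small if about 2% or fewer outcomes are missing, or if about two thirds of patients score 90 and loss is balanced. Error reaches roughly two to four times nominal at 10–20% missing when arm medians can vary. It also rises well above nominal when loss is unequal between arms, or depends on both arm and stratum, in the direction that favours metformin. This should be fixed before the ITT results and the secondary endpoints are relied on.

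**What to change.** Replace the imputation sentence in SAP 13.5 with rules of this kind:

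- Median imputation, if kept, applies only to named baseline covariates and never to outcomes.
- In the Bayesian model, a missing HFD-90 contributes no likelihood (valid under MAR given arm and stratum). Where death or a minimum number of inpatient days is known, it contributes an interval.
- Frequentist models use multiple imputation with Rubin's rules, including arm, surgical stratum, age, Risk Analysis Index, index length of stay and discharge disposition. The same imputation is a sensitivity analysis for the primary endpoint, because MAR may need more than arm and stratum.
- A delta or tipping-point analysis covers loss that depends on the outcome, which the likelihood approach does not protect against.
- Time-to-event endpoints are censored at last contact and never imputed.
- Missing outcomes are reported by arm.

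SAP 5 ties unblinding to finalisation of the SAP, and SAP 1.1 dates that at 06 September 2023. If unblinding has already happened, report the corrected analysis, dated and labelled, beside the result under the written rule.

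The cost is one SAP paragraph and some programming, with slightly wider intervals. No new data are needed.

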### **13.6. Multiple Comparisons**

No adjustment for multiple comparisons will be made, as the primary analysis model is for a single endpoint and secondary endpoints are intended to provide a broad statistical context for results of the primary analysis model.
